## BACKGROUND

Parosteal osteosarcoma is a low-grade, malignant bone tumor arising usually on the metaphyseal surface of a long bone. It accounts for about 4% of all osteosarcomas and although rare, it is the most common type of osteosarcoma of the surface of bone (1). Around 15-25% of cases reported in literature showed high-grade spindle cell areas, indicating progression to high-grade sarcoma (dedifferentiation) that may resemble conventional osteosarcoma or undifferentiated spindle or pleomorphic sarcoma (2-5). This progression (dedifferentiation) may be seen at the time of the first diagnosis or, more often, at the time of recurrence. The medullary involvement of the tumor evaluated on CT and MRI and confirmed on histological specimen is another important feature of parosteal osteosarcoma that has been described in a variable percentage of cases reported in literature (range, 28-48% of series published) (2-5). The presence of the medullary involvement could change the surgical treatment, even if it does not seem to have an impact on survival and on local recurrence or metastases, at difference to the presence of progression (dedifferentiation) areas and of inadequate surgical margins that are the most important prognostic factors in parosteal osteosarcoma reported in literature (1-5). This data should be verified in a wide series of parosteal osteosarcoma with an adequate follow-up, because the case series but two, reported in literature, are limited in terms of number of cases and of time of follow-up (4,5).

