## OBJECTIVE OF THE STUDY

The aim of the present study is to review all the cases with a diagnosis of primary parosteal osteosarcoma treated at the Rizzoli Institute from 1900 up to 31 July 2018, retrospectively.

The study will exam all the clinical, radiological, and histological features of this tumor with regard importance of medullary involvement, the types of treatment, the status of surgical margins, the presence of progression (dedifferentiation) areas and the relationship of these factors to individual outcome.

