### **MATERIAL AND METHODS**

We will retrieve from the database of the Rizzoli institute all the cases with a histological diagnosis of parosteal osteosarcoma from 01Jan1900 to 31Jul2018.

We aspect to find approximately 220 cases.

We will review all the medical records, radiological imaging, and histological data of these cases.

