### **STATISTICS**

To the case series will be applied a descriptive statistic.

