### **ENROLLMENT PROCEDURE**

Patients considered eligible will be included in the study, after providing a written informed consent.

Since we will include cases of several decades ago, and due to the high incidence of mortality of the disease under investigation, it would be possible that some eligible subjects will be deceased.

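### The published finding of no medullary effect on outcome is to be verified by description alone, so similar figures in the two groups could be taken as confirmation when events are too few to support it

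*Protocol*

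**What the plan says.** The Background states that medullary involvement could change the surgery, "even if it does not seem to have an impact on survival and on local recurrence or metastases", and contrasts it with dedifferentiation and inadequate margins, which it names as the main prognostic factors. It continues: "This data should be verified in a wide series of parosteal osteosarcoma with an adequate follow-up". The reason given is that all but two of the earlier series were small and had short follow-up.

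The Objective section includes the importance of medullary involvement among the features to be examined, together with "the relationship of these factors to individual outcome".

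Material and Methods gives the expected size: "We aspect to find approximately 220 cases". This is a retrieval estimate, with no event count or precision attached.

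The Statistics section is a single sentence: "To the case series will be applied a descriptive statistic".

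**The concern.** For medullary involvement, the finding to be verified is an absence of effect. Two groups can look alike because the factor does not matter or because too few events have occurred to show that it does. A table of proportions or a pair of survival curves without interval estimates looks much the same in both situations.

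The protocol criticises earlier series for limited numbers and follow-up, but its own method offers no way to show whether the same limitation applies to the new series. What is at stake is the prognostic conclusion: a report could state that the published finding has been confirmed for an outcome on which the data say little.

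**Working it through.** **Plan's own figure.** The 220 cases are a database count. No significance level, power, effect size or event rate stands behind the number, so there is no calculation to reproduce.

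**Inputs from the protocol**
- N = about 220 (Material and Methods).
- Share with medullary involvement p: "range, 28-48% of series published" (Background). This gives 220 × 0.28 = 61.6 and 220 × 0.48 = 105.6, so about 62 versus 158 up to 106 versus 114 cases.

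**Assumed inputs**
- Events D: no rate is given. I take 5%, 10%, 20% and 30% of 220 (11, 22, 44 and 66 events), and 50% (110 events) as a high case.
- A two-sided 95% interval and an unadjusted comparison in which all 220 cases can be analysed.

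**Hazard ratio scale.** SE(log HR) ≈ 1/√[D·p(1−p)], with p(1−p) = 0.28 × 0.72 = 0.2016 or 0.48 × 0.52 = 0.2496. At an observed hazard ratio of 1.0 the upper limit is exp(1.96 × SE). Example for D = 22 and p = 0.28: 22 × 0.2016 = 4.435, square root 2.106, 1.96/2.106 = 0.931, exp(0.931) = 2.54.

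| Events (share of 220) | 95% interval at HR 1.0, p = 0.28 | 95% interval at HR 1.0, p = 0.48 |
|---|---|---|
| 11 (5%) | 0.27-3.73 | 0.31-3.26 |
| 22 (10%) | 0.39-2.54 | 0.43-2.31 |
| 44 (20%) | 0.52-1.93 | 0.55-1.81 |
| 66 (30%) | 0.58-1.71 | 0.62-1.62 |
| 110 (50%) | 0.66-1.52 | 0.69-1.45 |

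**Chance of seeing a real effect** (Schoenfeld approximation, two-sided 5%). Power against a true hazard ratio of 2 is 31-37% at 22 events, 54-63% at 44 and 72-80% at 66. Against 1.5 it is 13-16%, 23-27% and 32-38%.

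**Chance of excluding an effect when there is none.** For 80% power, D = (1.96 + 0.84)² / [(ln M)²·p(1−p)]. Excluding M = 2 needs 82 events (p = 0.28) or 66 (p = 0.48). Excluding M = 1.5 needs 237 or 192, against about 220 patients in all. The values 2 and 1.5 are illustrations, not limits from the protocol.

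**Absolute scale.** With the same proportion r in both groups, the half-width of the 95% interval for the difference is 1.96·√[r(1−r)(1/n₁ + 1/n₂)]. At r = 10% it is 7.9-8.8 percentage points, at 20% it is 10.6-11.8, and at 30% it is 12.1-13.5. With 10% observed in each group, a difference of about 8-9 points would still not be excluded.

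**The case against.** **The protocol never says that similar figures will count as proof.** This is correct. The call for verification is Background rationale and also covers dedifferentiation and margins, where an effect is expected. The Objective speaks of examining relationships, not of demonstrating absence of effect. One can therefore say only that similar figures could be misread. A reader might infer that the plan will declare no impact on the strength of similar figures, but no section supports that.

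**Intervals and interpretation rules belong in an analysis plan, and description does not forbid intervals.** Partly right. A separate plan may exist, and descriptive reporting can include confidence limits. But the protocol itself fixes the method as descriptive, and an analysis plan that followed it literally would inherit the mismatch with the stated purpose.

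**Events may be plentiful.** The Enrollment Procedure section expects some patients to have died, "due to the high incidence of mortality of the disease under investigation", the Informed Consent section repeats this, and the case window runs from 1900 to 2018. At 110 events a doubling would be excluded at an observed ratio of 1.0. This stands for survival, so the shortage of information cannot be asserted for all three outcomes. The mortality remark says nothing about counts of local recurrence or metastasis.

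**There is no fixed event count below which verification is impossible.** A reader might infer one from the table, but its limits hold only for an observed ratio of 1.0. With 22 events and an observed ratio of 0.7, the upper limit is 0.7 × 2.31 = 1.6 to 0.7 × 2.54 = 1.8, which is below 2. No minimum event number should be written into the plan on this basis.

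**The link to surgery is looser than it looks.** The Background mentions the effect on surgical choice despite the apparent lack of prognostic impact. It does not say that a finding of no impact would alter treatment, so that consequence should not be claimed.

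**A formal equivalence margin for three outcomes is a heavy demand on a fixed retrospective series of a rare tumour.** This is a fair point. The remedy below does not require one.

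**Conclusion.** The concern holds in a limited form. The Background asks for verification of an apparent absence of effect, the Objective asks for the relationship to outcome, and the Statistics section offers description only. Without an estimate and its uncertainty, a sparse comparison could pass for confirmation.

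The size depends on the event count, which the protocol does not give. If events occur in about 10% of cases, identical observed hazards remain compatible with more than a doubling (upper limit 2.3-2.5). At 20-30% the limit is 1.6-1.9, and at 50% about 1.5. These limits assume an observed ratio of 1.0, 220 analysable cases, 28-48% involvement and no adjustment for other prognostic factors. Survival may be adequately informed; whether local recurrence and metastases are cannot be judged from the protocol.

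**What to change.** Extend the Statistics section by a few sentences. For each of survival, local recurrence and metastases, report:
- the medullary versus non-medullary effect estimate (hazard ratio, or difference at a fixed time);
- its 95% interval;
- the number of events.

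Add that absence of impact will not be described as verified when the interval still includes a material effect. In that case the report should say that an effect up to the upper limit is not excluded. Saying beforehand what size of effect would be material makes this sentence easier to apply, but a formal margin is not essential.

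No additional data are needed. The cost is that the conclusion for rarer outcomes may be inconclusive instead of verified.

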## OBJECTIVE OF THE STUDY

The aim of the present study is to review all the cases with a diagnosis of primary parosteal osteosarcoma treated at the Rizzoli Institute from 1900 up to 31 July 2018, retrospectively.

The study will exam all the clinical, radiological, and histological features of this tumor with regard importance of medullary involvement, the types of treatment, the status of surgical margins, the presence of progression (dedifferentiation) areas and the relationship of these factors to individual outcome.

## STUDY DESIGN

This is single institution cases series review of histological and clinical data

## POPULATION

### Inclusion criteria

- 1) Male and female patients treated at Rizzoli Institute from 01 Jan 1900 to 31 Jul 2018
- 2) Diagnosis of parosteal osteosarcoma

- 3) Written informed consent prior to any study-specific analysis and/or data collection

According to the Italian “*Autorizzazione generale n. 9/2016 al trattamento dei dati personali effettuato per scopi di ricerca scientifica*” of the Privacy Tutor (and the corresponding regulation in the other participating countries) the informed consent is not required to be obtained by the deceased subjects, as long as all the other enrolment criteria are met and the study has been approved by the Ethic Committee (refers to INFORMED CONSENT section)

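### Does pooling cases from 1900 onward make medullary involvement, described through CT and MRI, non-comparable and confounded with treatment era?

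*Protocol*

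**What the plan says.** Under Inclusion criteria the protocol takes "Male and female patients treated at Rizzoli Institute from 01 Jan 1900 to 31 Jul 2018". Material and Methods gives the same dates for the database retrieval and expects about 220 cases.

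The only description of medullary involvement is in the Background: "The medullary involvement of the tumor evaluated on CT and MRI and confirmed on histological specimen is another important feature of parosteal osteosarcoma". The same sentence gives its frequency in the literature ("range, 28-48% of series published"). The section then says the feature may alter the surgery but does not seem to affect survival, local recurrence or metastasis, and asks for verification in a wide series with adequate follow-up.

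The Objective lists the factors to be studied, "with regard importance of medullary involvement, the types of treatment, the status of surgical margins, the presence of progression (dedifferentiation) areas", and adds "the relationship of these factors to individual outcome". No primary factor or endpoint is named.

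On sources, Material and Methods says: "We will review all the medical records, radiological imaging, and histological data of these cases". Statistics plans descriptive methods only. Data Collection announces a study-specific case report form for each subject; it is not among the documents at hand, nor is any statistical analysis plan. The Enrollment Procedure section mentions decades-old cases only because some patients will have died. No section says how medullary involvement is classified when CT and MRI are absent, or separates results by calendar period.

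**The concern.** Set the enrolment window beside the Background and a mismatch appears: a feature described through CT and MRI is to be studied in a series that starts long before either existed. For early cases the classification must rest on plain films, the chart or whatever specimen remains.

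If an abstractor recorded no evidence of involvement as absence, two things would follow. The frequency would be too low. The not-involved group would also contain a surplus of old cases, with different surgery, margins and follow-up, so a comparison by medullary involvement would partly be a comparison of eras.

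This would touch a question the study was set up to answer. The Background wants the apparent lack of effect on outcome verified, and misclassifying involved cases as uninvolved tends to hide a real difference. The series could then seem to confirm the prior belief for the wrong reason.

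**Working it through.** **No figure of the plan to reproduce.** The 220 is an expected retrieval count, with no error rate, power or effect size behind it.

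**Inputs from the protocol.** Window 1 January 1900 to 31 July 2018, about 118.6 years; about 220 cases; published frequency 28-48%, midpoint 38%. At 28% and 48%, 220 cases give 220 × 0.28 = 62 and 220 × 0.48 = 106 involved.

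**Inputs that must be assumed.** The share *f* of cases without CT or MRI, and the fraction *s* of true involvement that histology or records still detect in them. The protocol gives neither, nor the distribution of cases by decade.

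**Frequency.** With true frequency *p*, the recorded frequency is *p*(*fs* + 1 − *f*). For *p* = 0.38:

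| *f* | *s* = 0 | *s* = 0.6 | *s* = 0.8 | *s* = 1 |
|---|---|---|---|---|
| 0.2 | 30% | 35% | 36% | 38% |
| 0.3 | 27% | 33% | 36% | 38% |
| 0.5 | 19% | 30% | 34% | 38% |

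Only the *s* = 0 column, where every case lacking CT and MRI is called negative, falls below the published 28%. At the ends of the published range, with *f* = 0.1-0.5 and *s* = 0.6-0.8, a true 28% is recorded as 22-27% and a true 48% as 38-47%. At *s* = 1 nothing changes.

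**Make-up of the not-involved group at *s* = 0.** The share of unassessable cases is *f* / (1 − 0.38(1 − *f*)): 0.2/0.696 = 29%, 0.3/0.734 = 41%, 0.5/0.81 = 62%.

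**If unassessable cases are set aside instead.** The frequency is not diluted, provided assessability is unrelated to involvement. The denominator falls to 220(1 − *f*) = 176, 154 or 110. The 95% half-width, 1.96√(0.38 × 0.62/*n*), goes from 6.4 points at 220 to 7.2, 7.7 or 9.1.

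**Comparison with outcome.** Assume no true effect and an event risk of 30% in older and 15% in newer cases (both assumed). The recorded involved group is a mix of *fps* older and (1 − *f*)*p* newer cases; the rest are recorded as not involved. At the extreme examined (*f* = 0.5, *s* = 0.6, *p* = 0.48):
- involved: (0.144 × 0.30 + 0.24 × 0.15)/0.384 = 20.6%
- not involved: (0.356 × 0.30 + 0.26 × 0.15)/0.616 = 23.7%
- odds ratio: 0.84

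Over *f* = 0.3-0.5 and *s* = 0.6-0.8 the pooled odds ratio is 0.84-0.94 instead of 1.00; at *s* = 1 it is 1.00. For scale, the extreme case gives about 17.4 events among 84.5 involved and 32.1 among 135.5 not involved. The standard error of the log odds ratio is √(1/17.4 + 1/67.1 + 1/32.1 + 1/103.4) = 0.34, against a shift of |ln 0.84| = 0.18.

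**Follow-up length.** With one constant hazard giving 10% at 5 years (−ln 0.9/5 = 0.021 per year), 15 years gives 1 − 0.9³ = 27%. The hazard and both durations are assumed. This contrasts two whole eras; it is not the bias in a comparison by medullary involvement, where each group mixes both eras.

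**Reading the text.** The Background says "The medullary involvement of the tumor evaluated on CT and MRI and confirmed on histological specimen", so its own description includes histology. Cases are retrieved by histological diagnosis, so some histology underlies each one, and the methods send the abstractor to records and histology as well as imaging. The CT and MRI phrase and the 1900 opening date therefore do not contradict each other.

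**The case for a change.** The strongest argument for a change is one of timing. Stratifying by era can wait for an analysis plan, but whether a case was assessable must be captured when the form is completed. If absent and not assessable share one code, no later analysis can separate them. The Background also gives the only description of the feature in the protocol, with no operational definition to replace it. Calling the study descriptive is no defence either: a descriptive frequency is biased by false negatives, and the Objective does relate the factors to outcome. The remedy would cost one code on a form.

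Most of this stands as advice on building the form. It does not show an error in the protocol. The form is announced but not shown, so that it lacks such a code is a guess. The study reads archived material, so a missing code can still be recovered from chart, films and slides. That old cases would be recorded as uninvolved is a conjecture about the abstractor's behaviour; the alternative, that they drop out, has a different consequence and does not lower the frequency.

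The remedy would also keep the full window, so the inclusion criterion would be unchanged. It would accept a specimen showing the medullary interface in place of CT or MRI, which concedes that lack of CT or MRI does not by itself make a case unassessable.

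**Conclusion.** The observation is correct but calls for no change. The protocol is silent on how to classify medullary involvement without CT or MRI and on reporting by calendar period. It prescribes neither coding such cases as negative nor a comparison that ignores era. Silence of this kind is ordinarily filled by the case report form and the analysis plan, and a pathologist or radiologist reviewing a century of material would sensibly record what could not be judged.

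The possible harm runs from none, if histology is adequate throughout, to a halving of the recorded frequency if half the cases lacked CT and MRI and all of those were called negative. With partial detection, the assumed inputs give a modest fall in frequency and a shift in the odds ratio of about half its standard error at the extreme examined. All of this rests on shares, detection rates, event risks and follow-up times that the protocol does not give; an opening date of 1900 does not show that many of the roughly 220 cases are old. The wide window is itself a fair choice, since the Background justifies the study by the limited size and follow-up of most published series.

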## INFORMED CONSENT

All patients will be informed, by the investigator, of the aims of the study, the possible risks and benefits that will derive from the study participation. \*

The Investigator must clearly inform that the patient is free to refuse participation in the study and that can withdraw consent at any time and for any reason.

They will be informed as to the strict confidentiality of their patient data, but that their medical records may be reviewed for trial purposes by authorized individuals other than their treating physician.

The informed consent procedure must conform to the ICH guidelines on Good Clinical Practice. This implies that "the written informed consent form should be signed and personally dated by the patient or by the patient's legally acceptable representative".

The Investigator must also sign the Informed Consent form, and will keep the original at the site and a copy of the original must be handed to the patient.

The competent ethics committee for each Institution participating to the study must validate local informed consent documents before the study can be opened. It will be emphasized that the participation is voluntary and that the patient is allowed to refuse further participation in the study whenever he/she wants. This will not prejudice the patient's subsequent care.

Due to the high incidence of mortality of the disease under investigation, it would be possible that some potential eligible subjects will be deceased.

In order to allow and promote the increase in the knowledge of this rare disease that could be beneficial for other patient that are or will be affected, according to the Italian "Autorizzazione generale n. 9/2016 al trattamento dei dati personali effettuato per scopi di ricerca scientifica" of

the Privacy Tutor and the corresponding regulation in the other participating country, as well as the EU General Data Protection Regulation 679/2016 (that will be applicable from 25 May 2018), the informed consent is not required to be obtained by the deceased subjects according the aforementioned laws/dispositions.

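### Consent is required of the living and waived for the deceased, so the reviewed set need not be all the cases, and entry can depend on all-cause vital status

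*Protocol*

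**What the plan says.** The Protocol's Objective of the Study opens: "The aim of the present study is to review all the cases". It goes on to name "the relationship of these factors to individual outcome" as part of what will be examined. Material and Methods says "We aspect to find approximately 220 cases" and then commits the team to reviewing the charts, images and histology of all those retrieved cases.

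Entry is governed elsewhere. The third inclusion criterion is "Written informed consent prior to any study-specific analysis and/or data collection". The Enrollment Procedure repeats it: "Patients considered eligible will be included in the study, after providing a written informed consent". The Inclusion criteria and the Informed Consent section make one exception: "the informed consent is not required to be obtained by the deceased subjects according the aforementioned laws/dispositions". Informed Consent also says that "the patient is free to refuse participation in the study and that can withdraw consent at any time and for any reason". No route is given for a living patient who cannot be traced, does not answer or declines.

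The Statistics section reads: "To the case series will be applied a descriptive statistic".

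**The concern.** The promise to review every retrieved case and the entry rule can both hold only if all living patients are found and agree. The Protocol's own right of refusal, which only the living can use, means this cannot be presumed.

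The gap is not neutral, because the entry rule turns on vital status. Deceased patients who meet the other criteria come in automatically, and living patients come in by consent. If survival is among the outcomes, selection acts on the outcome itself. That survival is an outcome is an inference: the Background discusses survival, local recurrence and metastasis and asks for confirmation in a large series, while the Objective speaks only of individual outcome.

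A descriptive analysis gives no protection, since plain proportions are what this kind of selection distorts most directly. A series of a rare tumour that is read as complete could mislead on mortality.

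**Working it through.** **Inputs.** From the Protocol: about 220 retrieved cases (Material and Methods), and a dedifferentiation frequency of 15-25% (Background), from which 20% is taken. The 220 is a database expectation with no power calculation behind it, so there is no figure to reproduce. Everything else is assumed, because the Protocol gives neither of these:

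- d = share of the retrieved cases who are dead
- c = share of the living who are traced and consent

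**Effect on the death share, if vital status is known for everyone.**

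Included number = 220 × [d + (1 − d)c]. Observed share dead = d / [d + (1 − d)c].

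| d | c | Included | Observed share dead | Shift (points) |
|---|---|---|---|---|
| 0.30 | 0.5 | 143.0 | 46.2% | 16.2 |
| 0.30 | 0.7 | 173.8 | 38.0% | 8.0 |
| 0.30 | 0.9 | 204.6 | 32.3% | 2.3 |
| 0.20 | 0.5 | 132.0 | 33.3% | 13.3 |
| 0.20 | 0.7 | 167.2 | 26.3% | 6.3 |
| 0.20 | 0.9 | 202.4 | 21.7% | 1.7 |

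At c = 1 there is no shift. For a shift of 5 points, solve d / [d + (1 − d)c] = d + 0.05, which gives c = [d/(d + 0.05) − d] / (1 − d):

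- d = 0.30: (0.857 − 0.30)/0.70 = 0.796
- d = 0.20: (0.80 − 0.20)/0.80 = 0.750

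**Effect on a factor-outcome relationship.** Assume 20% have dedifferentiation, with mortality 50% in those with it and 15% in those without. The true values are risk difference 0.35, risk ratio 3.3 and odds ratio 5.7. With c = 0.7 in both groups:

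- with the factor: 0.10 / (0.10 + 0.07) = 0.588
- without the factor: 0.12 / (0.12 + 0.476) = 0.201
- risk difference 0.387, risk ratio 2.92, odds ratio 5.67

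The risk difference and risk ratio move, and the odds ratio does not. If consent differs by factor, the odds ratio moves too:

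- c = 0.65 with and 0.75 without: (0.10 × 0.51) / (0.065 × 0.12) = 6.54
- c = 0.75 with and 0.65 without: (0.10 × 0.442) / (0.075 × 0.12) = 4.91

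**Bounds when vital status is not known for everyone.** Let N be the number retrieved, D the number included as deceased and A the number included as living. The death share of the retrieved series lies between D/N (all not included are alive) and (N − A)/N (all not included are dead). With N = 220, D = 66 and A = 108:

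- included 174, observed share 66/174 = 37.9%
- not included 220 − 174 = 46
- bounds 66/220 = 30.0% to 112/220 = 50.9%

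The observed 37.9% lies inside the bounds, so the error can go either way. The two shares are equal when 0.379 × 46 = 17.4 of the not included are dead. With 17 or fewer dead the included set overstates mortality, and with 18 or more it understates it. If 26 of the 46 were known to be alive and 20 stayed unknown, the bounds would narrow to 30.0% to 86/220 = 39.1%.

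**The case against.** **Scope.** Flow counts and sensitivity bounds often belong in an SAP or report, and the SAP is not shown. That is fair, and their absence from the Protocol is not the point. The point is that two stated rules conflict, in sections that define the aim and the population. That wording has to be settled in the Protocol.

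**The aim and the criteria can be read together.** An objective states an intention, the criteria decide who enters, and Data Collection asks for a CRF only for included subjects. This softens the Objective. It does not soften Material and Methods, which commits to reviewing all the retrieved cases.

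**All-cause death is not disease outcome.** The waiver depends on having died by the time of the study, from any cause. With treatment dates back to 1900, long survivors who later died of something else also enter without consent, and they are good disease outcomes. This stands. Disease-specific death, recurrence and metastasis are affected only as far as they are linked to all-cause vital status.

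**Direction.** A reader might infer that mortality is bound to be overstated. That follows only when vital status is known. Patients whose death is unknown to the site also drop out, and the lower bound, with all of the not included alive, may be unrealistic for early decades.

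**Materiality.** Neither d nor c is in the Protocol, and with nearly complete consent the shift is small. This also stands.

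**The fix removes no bias.** True. It changes what may be concluded, which is what can be done while the consent rule stays in place.

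**Conclusion.** The point holds as a conditional one. As written, the plan makes entry depend on all-cause vital status unless every living patient is included, while promising a review of all retrieved cases. Confidence is high for the mechanism and not for its size. Under assumed values and known vital status, a shift above 5 points needs fewer than about 80% of the living included (30% dead) or 75% (20% dead).

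Several stronger readings are tempting and are not supported. The waiver for the deceased is not an error. The figure of 220 is a retrieval estimate and not a wrong sample size. Nothing shows that consent will in fact be low. Associations are not all distorted: the odds ratio for death keeps its value if consent among the living is unrelated to the factor.

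This should be corrected because an outcome statement could mislead if read as that of the whole series. It does not invalidate the study.

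**What to change.** 1. In Objective of the Study and in Material and Methods, state that about 220 is the number expected to be retrieved and that the reviewed set is the deceased plus consenting living patients. Patients not known to be dead and without consent are not included.
2. Report three counts: retrieved, included as deceased, included as consenting living. Split the not included by vital status or era only if the approval covers that look-up.
3. Where an all-cause death proportion is reported, give the bounds D/N to (N − A)/N beside it.
4. Do not present absolute death or survival proportions, or risk differences and risk ratios by factor, as those of the complete institutional series. State that associations hold for the included set, and that carrying an odds ratio for death beyond it assumes consent unrelated to the factor.

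The consent rule stays unchanged. The cost is a sentence in each of two sections, three counts, a pair of bounds and a limit on interpretation; items 2 to 4 may sit in the Protocol, the SAP or the report. The minimum needs no look-up of people who have not consented, so it does not touch the rule of consent before data collection. Without the optional split the bounds stay wide. The downside is a smaller stated analysable number and more cautious outcome statements.
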